### **Timeline/Timing of Procedures Participants:**

All the testing procedures will be carried out in both intra- and extra-operative sessions; these procedures are described below in the section title '*Research Testing Procedures for both -- and Extra-operative Sessions*'. Healthy controls will be studied during extra-operative session, i.e. outside the operating room.

Patients who have chosen to have surgery may participate in up to three testing sessions. These testing sessions may include a session performed during the surgery; in the operating room (intra-operative session). Some patients will undergo one session prior to surgery, and/or another session after the surgery; these studies will be performed outside the operating room (extra-operative session).

Physiological monitoring of the central nervous system (CNS) will be carried out during both intra- or extra-operative sessions. CNS monitoring in the intraoperative sessions will include recordings of single neuron activity, local field potentials from microelectrode and surface electrodes, and the EEG. CNS monitoring in the extra-operative sessions will include EEG alone. Any intra- or extraoperative session may include monitoring through EKG electrodes, EMG electrodes, accelerometers, eye position sensors, and skin conductance monitors.

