- 6) **Muscle Contraction (Ischemia) Test:** The blood supply to the participant's arm appropriate to the side of the procedure or the side of psychophysical testing will be cut off by placing a standard blood pressure cuff on the participant's arm and inflating the cuff to 220 mm/Hg. Then, the participant will be asked to grip a handle repeatedly while the cuff is inflated. Finally, the participant will be asked to relax his/her hand while the cuff remains inflated for another one to two minutes.
- 7) **Electrical stimulation of the Skin:** an FDA approved constant current stimulator (DS7A, Digitimer, Hertfordshire, UK) or a constant current stimulator (S12, Grass, Warwick, RI , U.S.A.) will be applied to the hand to produce a non-painful tingling sensation. The electric stimulus will be delivered through a pair of Ag/AgCl electrodes filled with isotonic paste (9-mm diameter, Docxs Biomedical Products,

Date: February 19, 2023

Principal Investigator: [name].

Application Number: NA\_00079932

Ukiah, CA) placed on the wrist. The subject will be free to remove the electrodes from her/his hands at any time.

8) **tDCS Stimulation:** The tDCS portion of the experiment will begin with DC current (maximum of 2 mA) stimulation delivered through surface electrodes (TransQE from IOMED®, surface area: 25 cm^2) using a Phoresor® II Auto (Model No. PM850, IOMED®, Salt Lake City, Utah 84120, USA). In some experiments, one electrode will be positioned above the primary motor cortex of an affected side, the other electrode will be placed over the forehead. In other experiments, one will be positioned over the primary motor cortex of an affected side and the other one above the contralateral motor cortex. Anodal or cathodal tDCS will be delivered for 20 min. The current will be increased in a ramp-like fashion to reduce the appearance of transient phosphenes usually present with rapid on-off applications. Previous studies have demonstrated that these parameters of tDCS modulate motor cortical function for up to 90 minutes following the end of stimulation and in a study in stroke patients this stimulation elicited motor performance improvements that outlasted the stimulation period.

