For sham stimulation the electrodes will be placed in the same way as for real tDCS in the absence of real stimulation, this means stimulation will be increased to a current strength near the perception threshold and will be decreased afterwards and set to 0 mA output for a period of 20 min. With this procedure participants are usually unable to differentiate between tDCS and sham stimulation.

After prepping and draping the subject's scalp for the surgical procedure, the tDCS electrode arrays will be positioned approximately over the hand region of the motor cortex following the guidelines of (Edwards et al., 2013; Kou et al., 2012; Villamar MF et al., 2013). We employ surface electrodes (TransQE from IOMED®, surface area: 25 cm^2) connected to a conventional tDCS device using a Phoresor® II Auto (Model No. PM850, IOMED®, Salt Lake City, Utah 84120, USA) to deliver DC to the scalp via electrodes. The central active electrode is placed above the representational area of the ADM muscles (approximately over C3 or C4 based on the International 10/20 EEG System corresponding to the laterality of Parkinson symptoms) and the reference electrode is located in contralateral motor cortex. The microelectrode will be positioned in the target of interest (subthalamic nucleus or globus pallidus interna), and recordings of multiunit and field potential activity as a baseline will take place for 5 minutes. Application of tDCS will then be performed at a set current of 2 mA for 10 minutes. Recordings of multiunit and field potential activity will take place during the application of tDCS and for a period of 5 minutes after the cessation of the tDCS.

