### **Transcranial Direct Current Stimulation (tDCS) Device**

Date: February 19, 2023

Principal Investigator: [name].

Application Number: NA\_00079932

We employ surface electrodes (TransQE from IOMED®, surface area: 25 cm^2) connected to a conventional tDCS device Phoresor® II Auto (Model No. PM850, IOMED®, Salt Lake City, Utah 84120, USA) to deliver DC current to the scalp via surface electrodes.

tDCS will be administered with a current strength of 2 mA for maximum of 10 min by a constant current stimulator. Based on subject restrictions two types of electrode configuration will be applied:

1. Conventional rectangular sponge pad: we will use a pair of saline-soaked surface sponge electrodes (anode: 7 × 5 cm^2; cathode: 7 × 5 cm^2). The anode electrode will be positioned over the motor cortex representational area of the hand region on an affected side, and the return electrode will be placed above the contralateral motor cortex area.

2. 4 × 1 ring: The central active electrode will be placed above the representational area of the unaffected side hand (coinciding with the center of the anodal pad used for regular-pad stimulation) and surrounded by four return electrodes (each at a ring center to ring center distance of 3.5 cm from the active electrode) which will be connected to a four-to-one wire adaptor for the DC stimulator. Altogether five sintered Ag/AgCl ring electrodes (outer radius: 12 mm, inner radius: 6 mm) will be stabilized with plastic holders filled with EEG conducting gel (H + H Medical Devices, Germany and with gel-skin contact area ~25 ± 2.5 mm^2). Since the sensation to tDCS could differ with electrode and gel type (Minhas P, et al. 2010), here we will apply the suggested Ag/AgCl sintered ring electrodes (Minhas P, et al. 2010), and the conducting gel for less skin sensation as reported by the subjects.

Numerous methods utilize external landmarks to locate the motor strip (pre central gyrus). The motor strip typically lies anywhere from 4 to 5.4 cm behind the coronal suture. Based on the International 10/20 EEG system the C3 and C4 locations correspond to the left and right motor cortex (Edwards et al., 2013; Kido et al., 1980; Sarmento et al., 2008; Ebeling et al., 1987).

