## 7. Study Statistics

This is a single institution, long-term exploratory study to understand forebrain networks of human sensory processing and motor control. Specifically Objective I will address cortical and subcortical networks of sensory signaling and processing, while Objective II will address the cortical and subcortical networks involved in motor control.

Due to the exploratory nature of the study, all outcome data will be collected regardless of data type such as electrophysiological responses, or timing, or the questionnaires related psychological function. In general, data will be summarized using descriptive statistics and graphical techniques. Within and between-subjects comparisons will use paired and unpaired analysis, respectively. Longitudinal outcomes or repeated measures will be considered and possibly be analyzed using generalized linear model. Correlation coefficient or concordance correlation coefficient will be used to estimate correlation between two outcomes.

The outcome measures for the three objectives are indicated below:

Primary and secondary outcome variables:

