### ***Objective II and III:***

Our primary outcome variables will identify the functional connectivity within networks of cortical and subcortical structures which subserve movement. We will determine functional connectivity between structures activated during actual and imagined movement. Recordings will be made of single neuron and LFP activity in the basal ganglia, thalamus and cortex during actual and imagined movements.

Our secondary outcome variables will identify the functional connectivity within networks of cortical and subcortical structures which subserve movement disorders. We

Date: February 19, 2023

Principal Investigator: [name].

Application Number: NA\_00079932

will determine functional connectivity between structures activated during disordered movement. We will also determine the effects of tDCS on single and multiunit activity in the recorded subcortical structures. Recording and analysis techniques will be similar to those under the primary outcome of this objective.

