An animal study (rat) (Liebetanz et al., 2009), investigated the safety limits of extended transcranial direct current stimulation. Fifty-eight rats received single cathodal stimulation at 1–1000  $\mu$ A for up to 270 min through an epicranial electrode. Histological evaluation was performed 48 h later. A threshold estimate was calculated from volumes of DC-induced lesions. Brain lesions occurred at a current density of 142.9 A/m^2 for durations greater than 10 min. For current densities between 142.9 and 285.7 A/m^2, lesion size increased linearly with charge density; with a calculated zero lesion size intercept of 52400 C/m^2. Brains stimulated below either this current density or charge density threshold, including stimulations over five consecutive days, appeared the same as nonstimulated controls. The results of these systematic animal studies provide an estimate of a safety threshold for deleterious DC effects. With respect to the charge density, the upper limit used for these proposed human intraoperative studies is lower by two orders of magnitude.

One perceived limitation for the use of tDCS intraoperatively in subjects undergoing DBS lead placement is the resulting modification of current flow by the presence of surgical burr holes. Modeling studies can provide insight into how skull defects would affect current flow through the brain. Based on modeling results modifying the stimulation current intensity and changing the electrode location or electrode type can compensate for the effects (Datta et al., 2010). In the case of a craniotomy, there is a relatively highly conductive fluid pathway for current entering the brain, but it is highly dependent on the craniotomy position relative to the electrode montage used with tDCS. A small defect under the anode electrode leads to current flow in the cortex restricted to locations directly under the defect. A similar sized defect placed between the electrodes does not significantly alter current the flow pattern in comparison with a healthy head with no defect ( Datta et al., 2010).

The tDCS electrodes in this study will be placed at least 3 cm from the closest burr hole.

The psychological and neuropsychological tests are administered by pencil and paper or by a structured interview with a practicing psychiatrist or clinical psychologist.

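### tDCS durations conflict, the contrast for the unit-activity outcome is left open, and the stated charge-density margin does not hold for the 4 × 1 ring electrode

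*Combined protocol and SAP*

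**What the plan says.** All references are to the combined protocol and SAP.

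**Duration.** Section 4, item 8 (tDCS Stimulation) first describes active stimulation in general, at a maximum of 2 mA: "Anodal or cathodal tDCS will be delivered for 20 min". The sham described next is ramped up to near the perception threshold, brought down, and "set to 0 mA output for a period of 20 min". The intra-operative paragraph that follows has a 5 min baseline recording, then "Application of tDCS will then be performed at a set current of 2 mA for 10 minutes", with recording during stimulation and for 5 min afterwards. Section 6 (tDCS Device) says "tDCS will be administered with a current strength of 2 mA for maximum of 10 min by a constant current stimulator" and then lists two electrode configurations, a 7 × 5 cm sponge pair and a 4 × 1 ring.

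**Outcome and analysis.** Section 7, Objective II and III, includes under the secondary outcomes: "We will also determine the effects of tDCS on single and multiunit activity in the recorded subcortical structures". Section 4 (Timeline/Timing of Procedures) says "CNS monitoring in the extra-operative sessions will include EEG alone", so this outcome can come only from the operating room. The general rule in section 7 is "Within and between-subjects comparisons will use paired and unpaired analysis, respectively"; a generalized linear model is mentioned as a possibility for repeated measures.

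**Charge density.** Section 8 (Transcranial direct current stimulation) cites a rat study with a zero-lesion intercept of 52,400 C/m² and a lesion current density of 142.9 A/m². It states that, on charge density, "the upper limit used for these proposed human intraoperative studies is lower by two orders of magnitude". Section 8a, item iv, connects the ring with placement around the burr holes and says that total applied current will be reduced, without giving a figure.

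**The concern.** Three things are at stake.

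First, a 20 min instruction and an unqualified 10 min ceiling cannot both govern active stimulation. At 2 mA the delivered charge differs two-fold between them.

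Second, the unit-activity outcome needs a defined comparison. Intra-operative unit recordings can change over 20 min for reasons unrelated to stimulation. The only sham described is twice as long as the intra-operative active period and is not expressly assigned to that block. If it is used as it stands, the windows do not line up. If it is not used, a before/during/after change is open to being read as a tDCS effect when it may be drift.

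Third, section 8 gives one margin for all the intra-operative tDCS work, while section 6 lists electrodes whose contact areas differ greatly. A margin computed for a large pad does not carry over to a small ring.

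**Working it through.** **1. Durations side by side**

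| Place | Active | Sham |
|---|---|---|
| Section 4, item 8, general text | 20 min, maximum 2 mA | 20 min at 0 mA |
| Section 4, item 8, intra-operative block | 10 min, 2 mA | none expressly assigned |
| Section 6, tDCS Device | at most 10 min, 2 mA | not mentioned |

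The intra-operative block agrees with section 6. The general text does not. The sham mentioned in section 3 (Motor Control) belongs to a cited study.

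Charge = current × time: 0.002 A × 600 s = 1.2 C; 0.002 A × 1,200 s = 2.4 C. The second figure is a ceiling, because the general text gives 2 mA as a maximum.

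**2. Time windows**

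Counting from the end of the 5 min baseline, the active block runs from 0 to 10 min and its post-stimulation window from 10 to 15 min. Total recording is 5 + 10 + 5 = 20 min. If the 20 min sham had the same baseline and a 5 min post window, that window would fall at 20 to 25 min. The two post windows would not overlap.

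**3. Charge-density margin**

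Charge density = current × time ÷ contact area. Margin = 52,400 ÷ charge density.

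The plan's own figure comes first. For the 25 cm² electrode at 2 mA for 10 min: 1.2 C ÷ 0.0025 m² = 480 C/m², and 52,400 ÷ 480 = 109. The statement in section 8 is reproduced, so this is the same basis of comparison.

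Ring area from the printed radii (12 mm outer, 6 mm inner): π × (12² − 6²) = 339 mm². The printed contact area is about 25 ± 2.5 mm². The ratio is 339 ÷ 25 = 13.6.

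| Electrode (2 mA, 10 min) | Area | C/m² | Margin |
|---|---|---|---|
| Surface electrode | 25 cm² | 480 | 109 |
| Sponge pad | 35 cm² | 343 | 153 |
| Ring, from radii | 339 mm² | 3,537 | 14.8 |
| Ring, printed contact area | 25 mm² | 48,000 | 1.09 (0.98 to 1.20 over 22.5 to 27.5 mm²) |

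Sensitivity checks:

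- *Lower current.* Section 3 mentions 1 or 2 mA. At 1 mA the ring margin doubles to 29.6 (radii) or 2.2 (printed area).
- *Generous area.* If the whole 12 mm disc made contact (452 mm²), the margin would be 19.7 at 2 mA and about 39 at 1 mA.
- *Area needed.* A 100-fold margin at 2 mA for 10 min requires 1.2 C ÷ 524 C/m² = 0.00229 m², or 22.9 cm². No reading of the ring comes near this.
- *Longer duration.* At 2 mA for 20 min the margins are 54.6 (25 cm²), 76.4 (35 cm²), and 7.4 or 0.55 (ring).

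**4. Current density, the separate criterion**

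Ring at 2 mA: 0.002 ÷ 0.000339 = 5.9 A/m² from the radii, or 0.002 ÷ 0.000025 = 80 A/m² from the printed area. Both are below 142.9 A/m².

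**The case against.** **The comparison is not absent.** A reader might infer that the tDCS outcome has no comparison at all. The documents do not support that. A 5 min baseline with recording during and after stimulation is a within-patient comparison, and section 7 assigns paired analysis to such comparisons. Nor is a sham shown to be missing: its description comes directly before the intra-operative paragraph in the same item, so its scope is unclear. What stands is that section 7 does not say which contrast is meant, and that the sham, if it applies, has a different length.

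**Uncontrolled recording is a legitimate choice.** The study is exploratory and mainly descriptive, and this is one secondary outcome among several. That is fair. It makes the point one of stating and interpreting the contrast, and does not make the design invalid.

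**Section 6 may describe only the operating room.** Its montages fit that reading: the pad placement matches the intra-operative paragraph, the ring is linked to burr holes, and the forehead montage of the general text is not listed. The section does not say so, however, and its ceiling is worded without restriction.

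**The ring figure may rest on a slip.** The 25 mm² area disagrees with the radii in the same sentence, so 1.1-fold should not be taken as the main result. The intra-operative paragraph names only the 25 cm² electrode, and section 8a says total current is reduced. All of this is fair, but the radii alone give about 15-fold, and no reduced current is stated.

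**Stronger readings of the margin.** A reader might infer that the ring is unsafe. The documents do not show that. The thresholds come from rat epicranial electrodes, section 8 treats falling below either one as sufficient, and the ring is below the current-density criterion on both areas. Section 8 also cites human exposure at 25.46 A/m² for 20 min without skin damage, which is 25.46 × 1,200 = 30,552 C/m². The radii-based 3,537 C/m² lies well below this; the 48,000 C/m² from the printed area does not. A reader might also infer that the large pads fail at 20 min, but 55- and 76-fold still round to two orders of magnitude.

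**Side of stimulation.** The ring text refers to the unaffected-side hand where other text refers to an affected side. A reader might infer two different sites. Section 6 says that the ring centre coincides with the centre of the anodal pad, so this is at most a wording query.

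**Conclusion.** The point holds in three limited parts.

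1. Active duration is contradictory between section 4, item 8 (20 min) and section 6 (at most 10 min), with charge of 2.4 C against 1.2 C at 2 mA. The only sham is 20 min, against a 10 min intra-operative active block to which it is not expressly assigned.
2. The contrast for the effect of tDCS on unit activity is implied but not specified. Without a time-matched sham, a change over the 20 min recording cannot be separated from drift. The size of any drift cannot be estimated from the documents.
3. The two-orders-of-magnitude margin holds for the 25 cm² and 35 cm² electrodes at 2 mA for 10 min (109- and 153-fold). It does not hold for the ring: about 15-fold from the radii or about 1.1-fold from the printed area, and about 30- or 2-fold at 1 mA.

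Part 3 assumes that the one central ring electrode carries the full current. Section 6 states 2 mA before listing both configurations, which supports this but does not settle it. The densities are at the electrode contact, the same basis that reproduces the plan's own figure. The finding is an unsupported stated margin and is not a judgement on safety.

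**What to change.** - Reconcile section 4, item 8 (general text, sham, intra-operative block) with section 6 on active and sham duration, and say which setting each statement governs. No value is proposed here.
- In section 7, state whether the tDCS outcome is active versus sham or within-patient before/during/after. If sham is used, compare change from the 5 min baseline over matched time windows, with the patient as the unit of analysis. If it is not used, report the change as uncontrolled.
- In section 6, reconcile the ring's contact area with its radii and state the current used with the ring.
- In section 8, restate the charge-density margin separately for each electrode and duration that is kept.
- Optionally, clarify whether the affected and unaffected side mean body side or hemisphere.

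The cost is protocol and SAP wording plus one recalculated figure. No new arm, visit, exclusion or data field is needed. The downside is a more cautious tDCS conclusion where there is no sham, and a less favourable stated margin for the ring.

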An approach that has been attempted recently for PD symptom control is transcranial direct current stimulation (tDCS). tDCS is a non-invasive procedure in which direct current (typically 1-2mA) is passed through anode and cathode electrodes that are placed on the head and localized using MRI, transcranial magnetic stimulation (TMS), or EEG. tDCS was first used by Fregni et al. on PD patients. They examined patients in the moderate stage who were off medication for 12 hours and found that application of anodal tDCS over the left primary motor cortex (M1) produced 20% improvement of clinical motor scores (as compared to sham stimulation). In this proposal, we will investigate the effects of tDCS on neuronal activity of the deep nuclear structures and also changes in phase –amplitude coupling at the cortical level (de Hemptinne et al., 2015) to seek possible explanations for the mechanism of action of DC stimulation.

Tonic pulsed motor cortex stimulation was introduced in early 1990 for the relief of chronic facial pain (Tsubokawa et al., 1991a, b) and recently, its use has been extended to exploration in patients with movement disorders. There is some evidence that direct cortical stimulation of the motor cortex through strip electrode contacts may relieve the motor symptoms of patients with PD (Canavero et al., 2002, 2003; Pagni et al., 2005, 2005). It may also provide some benefit for patients with PD during concurrent STN-DBS after chronic implantation and in long-term follow-up (Cioni, 2007, Meglio and Cioni, 2009). Motor cortex stimulation is highly influenced by DBS technology and in some studies uses a similar pulse generator. The stimulation pulse trains are similar to DBS systems, with similar adjustable parameters (Canavero et al. 2002, 2003; Cilia et al. 2007, 2008; Fasano et al. 2008; Gutierrez et al. 2009; Pagni et al. 2005; Strafella et al. 2007; Tani et al. 2007).

In order to investigate the neurophysiological role of the basal ganglia in speech production and control, subjects will perform speech production tasks intraoperatively. For each recording site, this will generate the data needed to characterize the scale and level of encoding and gain effects within single neurons, their surrounding local field potential (LFP), and their synchrony with sensorimotor cortex electrocorticography (ECoG).

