9) **Direct Cortical Stimulation:** The contacts from the subdural strip electrode, which is placed on the hand motor area, are utilized in either a unipolar or a bipolar configuration to deliver the stimulation current. The stimulation parameters will roughly fall into the ranges (amplitudes from 2 mAmp to 6 mAmp, rates from 10 Hz to 130 Hz, and pulse widths from 60  $\mu$ sec to 450  $\mu$ sec) (Canavero et al., 2003; Canavero et al., 2002; Cilia et al., 2007; Cilia et al., 2008; Fasano et al., 2008; Gutierrez et al., 2009; Pagni et al., 2005; Strafella et al., 2007; Tani et al., 2007). Direct cortical stimulation will be delivered by either the Alpha Omega NeuroOmega data acquisition system (Nazareth, Israel), or the Blackrock Microsystems NeuroPort data acquisition system incorporating the CereStim applicance (Salt Lake City, UT).

Date: February 19, 2023

Principal Investigator: [name].

Application Number: NA\_00079932

10) **Auditory Stimulation and Speech Testing:** A conventional speaker including earphones will be used to produce auditory stimulation and a high quality microphone will be used to record the sound of the subjects in the speech production task. In some tasks, participants will repeatedly read aloud syllable triplets, in which each triplet will be composed of items drawn from a pool of 16 syllables. The subject's voice may be recorded, and also played back to them using an earphone. Stimuli: The "basis set" for many experiments will be 4 consonants and 4 vowel phonemes, chosen such that they comprise different combinations of 5 articulator features, and 8 major phonetic state spaces (4 C and 4 V; lower portion of grid) described in human motor cortex. These will be combined to create 16 unique CV syllables, which vary in the frequency of occurrence and lexical status. The composition of this stimulus set will allow us to probe for multiple levels of encoding in the context of a single speech production task and acquired datasets. Other stimuli will also be used consisting of speech segments and tone sequences with similar outcome measures of correlation with the neural recordings.

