#### Studies of Cortical Stimulation in Parkinson's Disease

Cortical stimulation for the treatment of Parkinson's disease has been investigated recently (Lefaucheur, 2009). Here, cortical stimulation is mostly performed after chronic implantation of strip electrodes over the motor cortex. Following closure of the craniotomy, the electrode cable(s) are connected to a trial stimulator. Based on over 3–14 days of test stimulation, the best stimulation parameters and electrodes are decided in terms of improvement in Parkinson's symptoms. Among the total number of 37 Parkinson's disease patients that enrolled in a motor cortex stimulation study, the occurrence of epileptic seizures has been reported during test stimulation in a minority of patients N=1, Arle et al., 2008).

Date: February 19, 2023

Principal Investigator: [name].

Application Number: NA\_00079932

In this group of studies, most neurosurgeons attempted intraoperative test stimulation by using subdural grid electrodes. Test bipolar stimulation (210-1000  $\mu$ s –generally 400-500- $\mu$ s, 1-5 Hz up to 100Hz, with intensities up to 50 mA, anodally, and also cathodally) was applied by means of the contacts situated over the primary motor or sensory cortex. There were no other complications caused by the device or the implant procedure, and all patients tolerated the implantation procedure well. (De Rose et al., 2012; Canavero, 2015; Tani, and Saitoh, 2016). In contrast to these tonic stimulation studies, our proposed phase-dependent stimulation techniques represent a much narrower (reduced number of pulses) and much more transient (active only during specific bandpass power changes) (Chen et al., 2011, 2013) form of cortical pulsed stimulation, and we feel the chance of seizure production will be reduced for these reasons. The application of cortical stimulation is performed solely for research reasons as outlined here, to assess changes in subthalamic nucleus activity (Kim et al., 2008; Magill et al., 2001), and to assess possible clinical benefits for phase-dependent stimulation modalities. Since there is a risk of seizure with cortical stimulation, an IV antiepileptic (usually levetiracetam) ( Zachenhofer et al., 2011; Bahr et al., 2012; Kirmani et al., 2014; Jin et al., 2012) will be administered at the start of the surgical procedure. This is performed routinely for DBS lead placement procedures at Johns Hopkins due to the already present risk of seizures with the surgery.

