### Studies of Cortical Stimulation in Patients with Epilepsy

Rates of stimulation induced seizures have been measured in patient groups with and without symptomatic epilepsy concomitant with a brain tumor. Szelényi et al. used stimulation currents up to 40 mA, and found that 1/63 (1.6%) patients in the symptomatic epilepsy group suffered a stimulation induced seizure (Szelényi et al., 2007). In the nonsymptomatic group, similarly, 1/66 (1.5%) suffered a stimulation induced seizure. The range of reported seizure induction for intraoperative stimulation is from 1.2% (for a train of five stimulation technique) up to 9.5% for continuous 60 Hz stimulation (Szelényi et al., 2007). Zangaladze et al. also studied a series of invasively monitored patients undergoing cortical stimulation for mapping and used stimulation currents up to 17.5 mA at several stimulation frequencies (5-50Hz) (Zangaladze et al., 2008). These authors found that the production of neighboring electrode after discharges (which herald the onset of a seizure) are greatly reduced with lower stimulation frequencies while the actual cortical mapping is just as sensitive (Zangaladze et al., 2008). To further clarify, these stimulation induced seizure estimates occur in patients with known seizures or epilepsy. Subjects considered for this study do not have seizure disorders, and will be excluded from stimulation studies if there is a history of any seizure episode. Of note, a similar stimulation protocol involving phase dependent stimulation in epilepsy patients has been approved by the Johns Hopkins IRB under Protocol # IRB00040308.

The use of stimulation in the protocol described in this grant is much less intense than stimulation paradigms typically used for mapping. Phase-dependent stimulation techniques use subthreshold stimulation current levels timed to transiently measured periods of rhythmic activity generally lasting for only a few seconds. Monitoring for after discharges in neighboring electrodes will be used as a stopping point for further stimulation. After discharge monitoring is used routinely in the epilepsy community as a sign to abort cortical stimulation at a particular electrode (Lesser et al., 1999; Motamedi et al., 2002 ; Ojemann et al., 1989, 1991). Stimulation testing will be aborted and no further testing will be performed on subjects exhibiting after discharges.

Date: February 19, 2023

Principal Investigator: [name].

Application Number: NA\_00079932

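### The direct cortical stimulation procedure does not carry the phase-dependent, subthreshold and transient limits on which the Risks section rests its reduced-seizure argument

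*Combined protocol and SAP*

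**What the plan says.** **Procedure.** Section 4, item 9 (Direct Cortical Stimulation) delivers current through the subdural strip in a unipolar or bipolar configuration. Its limits are approximate: "The stimulation parameters will roughly fall into the ranges", namely "amplitudes from 2 mAmp to 6 mAmp, rates from 10 Hz to 130 Hz", with pulse widths of 60 to 450 microseconds.

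**Background.** Section 3, Objective II (Motor Control), introduces tonic motor cortex stimulation and says of it: "The stimulation pulse trains are similar to DBS systems, with similar adjustable parameters". The references attached to that statement are the ones item 9 cites for its ranges.

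**Risks.** Section 8, on Parkinson's disease, describes something else: "In contrast to these tonic stimulation studies, our proposed phase-dependent stimulation techniques represent a much narrower (reduced number of pulses) and much more transient". It concludes that "we feel the chance of seizure production will be reduced for these reasons". The subsection on patients with epilepsy adds: "Phase-dependent stimulation techniques use subthreshold stimulation current levels timed to transiently measured periods of rhythmic activity", with such periods generally lasting a few seconds, and calls the stimulation much less intense than mapping. Section 8a, item vi, names phase-dependent selective pulses as the one addition to the risks already present in awake lead placement, and caps current at 6 mA.

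**The concern.** The features that carry the reduced-risk argument (phase gating, fewer pulses, short delivery, subthreshold current) appear only in Section 8. Item 9, the only text that sets rate and pulse width, includes none of them, and its references are those used for DBS-like tonic trains, the type of stimulation with which Section 8 contrasts the proposed technique.

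Two things are at stake. First, the protocol says this stimulation is done solely for research and acknowledges a seizure risk. Anyone weighing that risk would do so on a description that the procedure does not enforce. Second, Section 3 asks how cortical stimulation affects phase-amplitude coupling and motor symptoms, and Section 8 seeks possible benefit from phase-dependent modalities. Gated and ungated pulses are different interventions for those questions. If both were delivered and the mode were not recorded, the results could not be separated afterwards.

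**Working it through.** No sample size, power or event calculation underlies this point, so the check is a comparison of the current text, with small side calculations.

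**Feature by feature**

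| Feature | Section 4, item 9 | Section 8 | Agree? |
|---|---|---|---|
| Current | about 2 to 6 mA | at most 6 mA | Yes, on the upper limit |
| Phase trigger | not stated | phase-dependent | No |
| Duration or pulse count | not stated | fewer pulses, transient, a few seconds | No |
| Threshold | not stated | subthreshold, with no definition in mA | Cannot be checked |
| Rate | about 10 to 130 Hz | none set for this study; cited data up to 100 Hz | Upper rate not covered |

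The equipment description in Section 6 does not fill the gap. One stimulator lets the user set the number of pulses, amplitude and frequency, but no limit is given and no phase trigger is mentioned.

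**Rates and currents cited under Risks.** Test stimulation in Parkinson's disease went up to 100 Hz and 50 mA. One mapping series used 5 to 50 Hz at up to 17.5 mA; another used up to 40 mA. The top of the quoted range of intraoperative seizure rates is "up to 9.5% for continuous 60 Hz stimulation". Item 9's 130 Hz is above all of these rates, and its 6 mA is below all of these maximum currents.

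**Cited seizure counts** (exact Clopper-Pearson 95% intervals)

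- Parkinson's motor cortex stimulation: 1/37 = 2.7% (0.07% to 14.2%); the protocol gives no percentage.
- Mapping, symptomatic epilepsy: 1/63 = 1.59%, stated as 1.6% (0.04% to 8.5%).
- Mapping, no symptomatic epilepsy: 1/66 = 1.52%, stated as 1.5% (0.04% to 8.2%).

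The two stated percentages reproduce. With one event each, the series cannot establish how risk changes with mode.

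**Why duration matters.** Pulse count = rate × time. The durations here are assumptions, because item 9 gives none. I take 3 s for a burst of a few seconds and 60 s for an ungated train.

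- At 10 Hz: 10 × 3 = 30 and 10 × 60 = 600 pulses.
- At 130 Hz: 130 × 3 = 390 and 130 × 60 = 7,800 pulses.

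Item 9 as written excludes none of these. They illustrate exposure and are not risk estimates.

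**The case against.** The strongest reply is that the document should be read as a whole. Gated trains also need an amplitude, a rate and a pulse width, so item 9's ranges are compatible with phase-dependent delivery. Section 8 describes that technique as the one proposed. On this reading there is a single mode and a missing cross-reference. That is possible, and the documents do not establish that any patient will receive both modes. But item 9 does not impose the limits, and its references point to tonic stimulation, so the reader cannot tell which reading is intended.

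A reader might also infer that the safety case covers only brief, gated, subthreshold pulses and so fails for the procedure altogether. The documents do not support that. Section 8 also cites tonic and continuous stimulation at higher currents. The exclusion for seizure history or seizure-provoking medication, the intravenous antiepileptic, and after-discharge monitoring with testing stopped all apply whatever the pulse pattern. Phase dependence is argued as a reason for reduced risk; it is not the whole safety basis.

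Nor do the quoted seizure rates, 1.2% for a train of five to 9.5% for continuous 60 Hz, measure gated against ungated risk at 2 to 6 mA. They compare mapping techniques, and the protocol attributes its estimates to patients with known seizures or epilepsy, who are excluded from stimulation here. Likewise, 130 Hz against 60 Hz is a ratio of rates, not of risks.

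Finally, a reader might infer that the plan pools all cortical stimulation into one effect. Section 7 specifies no analysis of direct cortical stimulation, pooled or otherwise.

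**Conclusion.** The point holds as an inconsistency between procedures and risks. Item 9 permits stimulation without the gating, brevity and subthreshold conditions from which Section 8 argues that seizures are less likely and that stimulation is much less intense than mapping. 'Subthreshold' has no stated meaning, so the documents do not show that 2 to 6 mA satisfies it. Permitted rates above 100 Hz, up to 130 Hz, exceed any stimulation rate cited under Risks. The current cap is consistent and the general safeguards stand.

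The size of any added seizure risk is unknown and cannot be derived from the documents. The conclusion assumes that item 9 governs what is delivered, since no other text sets rate and pulse width. It takes no view on which stimulation setting is right.

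**What to change.** 1. Reconcile Section 4, item 9 with Section 8 (both cortical stimulation subsections and Section 8a, item vi) so that they describe the same mode or modes, including whether delivery is phase-gated and what bounds its duration or pulse count.
2. State what 'subthreshold' means and how it is established for a patient.
3. Make the risk statement cover the most intense stimulation that the procedure still permits, including its highest rate.
4. If more than one mode is kept, record the mode for each stimulation block so that results can be reported by mode.

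The choice of settings is for the investigators and the ethics board. The cost is protocol wording and, if several modes remain, one recorded variable. The downside of reporting by mode is smaller groups, which is tolerable in a study that calls itself exploratory and plans mainly descriptive summaries.
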